### **5.2.2 Timing of Dose Administration**

MK-3475 should be administered on Day 1 of each cycle as a 30-minute IV infusion (25-40 min) every 3 weeks (Q3W) after all procedures/assessments have been completed as detailed on the Trial Flow Chart (Section 6.0), except for the post-infusion PK sample time points listed in the Trial Flow Chart. Sites should make every effort to target infusion timing to be as close to 30 minutes as possible. MK-3475 may be administered up to 3 days before or after the scheduled Day 1 of each cycle due to administrative reasons only.

All trial treatments will be administered on an outpatient basis. The specific time of trial treatment infusion (e.g., time of the week for first administration; time of the day for each administration) should take into consideration PK sampling time points and study visit procedures.

### **5.2.3 Trial Blinding/Masking**

This is an open-label trial; therefore, the Sponsor, investigator and subject will know the treatment administered.

## **5.3 Randomization or Treatment Allocation**

Subjects participating in this trial will be allocated by non-random assignment.

## **5.4 Stratification**

No stratification based on age, sex or other characteristics will be used in this trial.

## **5.5 Concomitant Medications/Vaccinations (Allowed & Prohibited)**

Medications or vaccinations specifically prohibited in the exclusion criteria are not allowed during the ongoing trial. If there is a clinical indication for any medication or vaccination specifically prohibited during the trial, discontinuation from trial therapy or vaccination may be required. The investigator should discuss any questions regarding this with the Sponsor Clinical Director. The final decision on any supportive therapy or vaccination rests with the investigator and/or the subject's primary physician. However, the decision to continue the subject on trial therapy or vaccination schedule requires the mutual agreement of the investigator, the Sponsor and the subject.

### **5.5.1 Allowed Concomitant Medications**

All treatments that the investigator considers necessary for a subject's welfare may be administered at the discretion of the investigator in keeping with the community standards of medical care. All concomitant medication will be recorded on the case report form (CRF) including all prescription, over-the-counter (OTC), herbal supplements, and IV medications and fluids. If changes occur during the trial period, documentation of drug dosage, frequency, route, and date may also be included on the CRF.

All prior/concomitant medications received within 4 weeks before the first dose of trial treatment and 30 days after the last dose of trial treatment should be recorded. Concomitant medications administered after 30 days after the last dose of trial treatment should be recorded for SAEs and ECIs as defined in Section 7.2.

### **5.5.2 Prohibited Concomitant Medications**

Subjects are prohibited from receiving the following therapies during the Screening and Treatment Phase (including retreatment for post-complete response relapse) of this trial:

- Antineoplastic systemic chemotherapy or biological therapy
- Immunotherapy not specified in this protocol
- Investigational agents other than MK-3475
- Radiation therapy
  - Note: Radiation therapy to a symptomatic solitary lesion or to the brain may be allowed after consultation with Sponsor.
- Live vaccines within 4 weeks prior to the first dose of trial treatment and while participating in the trial. Examples of live vaccines include, but are not limited to, the following: measles, mumps, rubella, chicken pox, yellow fever, rabies, BCG, and typhoid (oral) vaccine. Seasonal influenza vaccines for injection are generally inactivated flu vaccines and are allowed.
- Glucocorticoids for any purpose other than to modulate symptoms from an event of clinical interest of suspected immunologic etiology.
  - Note: The use of physiologic doses of corticosteroids may be approved after consultation with the Sponsor.

Subjects who, in the assessment by the investigator, require the use of any of the aforementioned treatments for clinical management should be removed from the trial. Subjects may receive other medications that the investigator deems to be medically necessary. Local surgery or radiation therapy (if indicated for palliative measure only after discussion with the SPONSOR) may be permitted beyond Week 24 tumor assessment.

The Exclusion Criteria describes other medications which are prohibited in this trial.

There are no prohibited therapies during the Post-Treatment Follow-up Phase.

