## 1.0 TRIAL SUMMARY

Abbreviated Title	Phase Ib Study of MK-3475 in Subjects with Advanced Melanoma
Trial Phase	Ib
Clinical Indication	The treatment of subjects with locally advanced or metastatic melanoma
Trial Type	Interventional
Type of control	No treatment control
Route of administration	Intravenous
Trial Blinding	Unblinded Open-label
Treatment Groups	MK-3475 2 mg/kg every 3 weeks (Q3W)
Number of trial subjects	Approximately 35 subjects will be enrolled.
Estimated duration of trial	The sponsor estimates that the trial will require approximately 10 months from the time the first subject signs the informed consent until the last subject's last visit.
Duration of Participation	Each subject will participate in the trial from the time the subject signs the Informed Consent Form (ICF) through the final protocol-specified contact. After a screening phase up to 4 weeks, eligible subjects will receive treatment on Day 1 of each 3-week dosing cycle. Treatment with MK-3475 will continue until the subject meets the discontinuation criteria such as 24 months of therapy completion, documented disease progression (per modified RECIST 1.1), or unacceptable toxicity, etc. Subjects who meet criteria for temporary discontinuation of study therapy after complete response (CR) may consider stopping trial treatment. These subjects may be eligible for re-treatment after experiencing disease progression at the discretion of the investigator if they meet the criteria for re-treatment for up to one year; this will be designated the Second Course Phase. After the end of treatment, each subject will be followed for a minimum of 30 days for adverse event monitoring (serious adverse events will be collected for up to 90 days after the end of treatment). Subjects who discontinue for reasons other than disease progression will have post-treatment follow-up for disease status until initiating a non-study cancer treatment (including the treatment of marketed product of MK-3475), disease progression, withdrawing consent, death, or the end of the study. All subjects will be followed by telephone for overall survival until death, withdrawal of consent, or the end of the study.

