Treatment with MK-3475 will continue unless the subject meets the discontinuation criteria such as disease progression (evaluated by modified RECIST 1.1), unacceptable toxicity, or completion of 24 months of treatment with MK-3475 (refer to Section 5.8 for further details). Subjects who attain an investigator-determined confirmed CR may consider stopping trial treatment after receiving at least 24 weeks of treatment (Treatment Phase). Subjects who discontinue after at least 24 months of therapy for reasons other than disease progression or intolerance or who discontinue after attaining a CR may be eligible for up to one year of retreatment (Second Course Phase) after they have experienced radiographic disease progression. The decision to retreat will be at the discretion of the investigator only if no cancer treatment (including the treatment of marketed product of MK-3475) was administered since the last dose of MK-3475, the subject still meets the safety parameters listed in the Inclusion/Exclusion criteria and the trial remains open (refer to Section 7.1.5.2.1 for further details). After the end of treatment in Treatment Phase and Second Course phase, each subject will be followed for 30 days for adverse event monitoring (serious adverse events will be collected for 90 days after the end of treatment). Subjects who discontinue treatment for reasons other than disease progression will have post-treatment follow-up for disease status until initiating a non-study cancer treatment, disease progression, withdrawing consent, death, or the end of the study, whichever occurs first. Response and progression in the Second Course Phase will not count towards the ORR and PFS of the efficacy endpoint in

this trial. All subjects will be followed by telephone contact for overall survival until death, withdrawal of consent or the end of the study, whichever comes first. Clinical data may temporarily be locked to assess the efficacy endpoint, ORR per RECIST 1.1 for advanced melanoma when once all of the enrolled subject has either progression disease or has had an imaging 24 weeks after treatment initiation, whichever occurs first.

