### **5.7.3 Use in Pregnancy**

If a subject inadvertently becomes pregnant while on treatment with MK-3475, the subject will immediately be removed from the study. The site will contact the subject at least monthly and document the subject's status until the pregnancy has been completed or terminated. The outcome of the pregnancy will be reported to the SPONSOR without delay and within 24 hours if the outcome is a serious adverse experience (e.g., death, abortion, congenital anomaly, or other disabling or life-threatening complication to the mother or newborn). The study investigator will make every effort to obtain permission to follow the outcome of the pregnancy and report the condition of the fetus or newborn to the SPONSOR.

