## **5.8 Subject Withdrawal/Discontinuation Criteria**

Subjects may withdraw consent at any time for any reason or be dropped from the trial at the discretion of the investigator should any untoward effect occur. In addition, a subject may be withdrawn by the investigator or the Sponsor if enrollment into the trial is inappropriate, the trial plan is violated, or for administrative and/or other safety reasons. Specific details regarding discontinuation or withdrawal procedures; including specific details regarding withdrawal from Future Biomedical Research, are provided in Section 7.1.4 – Other Procedures.

A subject must be discontinued from the trial for any of the following reasons:

- The subject or legal representative (such as a parent or legal guardian) withdraws consent.
- The marketing approval of MK-3475 for melanoma, the completion of all safety follow-up or the time when a possibility of entry to second course is lost (e.g. the time of decision by investigator or subject for no enter to second course, the start of a new anti-cancer therapy, the delivery of marketed product of MK-3475 in each site, 6 months from marketing approval), whichever occurs last

A subject must be discontinued from treatment (but may continue to be monitored in the post-treatment follow-up portion of the trial) for any of the following reasons:

- Radiographic disease progression

Note: A subject may be granted an exception to continue on treatment with confirmed radiographic progression if clinically stable or clinically improved, please see Section 7.1.3.4

- Unacceptable adverse experiences as described in Section 5.2.1.2
- Intercurrent illness that prevents further administration of treatment
- Completed 24 months of treatment with MK-3475

Note: 24 months of study medication is calculated from the date of first dose. Subjects who stop MK-3475 after 24 months may be eligible for up to 1 year of additional study treatment if they progress after stopping study treatment provided they meet the requirements detailed in Section 7.1.5.2.1.

- Investigator's decision to withdraw the subject
- The subject has a confirmed positive serum pregnancy test
- Noncompliance with trial treatment or procedure requirements

- The subject is lost to follow-up
- Administrative reasons
- The delivery of marketed product of MK-3475 in each site
- 6 months from marketing approval for melanoma

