#### **7.1.5.4.3 Survival Follow-up**

Once a subject experiences confirmed disease progression or starts a new anti-neoplastic therapy, the subject moves into the survival follow-up phase and should be contacted by telephone every 12 weeks to assess for survival status until death, withdrawal of consent, or the end of the study, whichever occurs first.

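### Sections 5.5.2 and 5.7.3 remove subjects from the trial, while other sections stop treatment only and follow everyone for survival; a literal reading would censor OS, partly for prognosis-related reasons

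*Combined protocol and SAP*

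**What the plan says.** Two sentences take subjects out of the trial:

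- Section 5.5.2, on therapies prohibited during Screening and Treatment (including retreatment), says that subjects who in the investigator's assessment "require the use of any of the aforementioned treatments for clinical management should be removed from the trial".
- Section 5.7.3 says that if a subject becomes pregnant on treatment, "the subject will immediately be removed from the study".

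Other current text separates treatment from trial participation:

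- Section 1.0: "All subjects will be followed by telephone for overall survival until death, withdrawal of consent, or the end of the study". Section 2.1 repeats it: "All subjects will be followed by telephone contact for overall survival until death, withdrawal of consent or the end of the study".
- Section 5.5, the parent of 5.5.2, says only that "discontinuation from trial therapy or vaccination may be required".
- Section 5.8 opens its second list with "A subject must be discontinued from treatment (but may continue to be monitored in the post-treatment follow-up portion of the trial". That list includes "The subject has a confirmed positive serum pregnancy test".
- Section 7.1.5.4.3: "Once a subject experiences confirmed disease progression or starts a new anti-neoplastic therapy, the subject moves into the survival follow-up phase". Section 7.1.1.6.3 and note 3 to the flow chart in Section 6.1 agree.

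On analysis, Tables 8 and 9 make OS a secondary Kaplan-Meier summary in the FAS, censored at last assessment. No OS hypothesis is tested.

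**The concern.** A site has two incompatible instructions for the same subject. If it follows 5.5.2 to the letter, it closes the subject and stops collecting vital status. The OS analysis then censors that subject at the last contact.

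Kaplan-Meier estimation assumes that censored subjects have the same later risk as those still followed. A subject who needs other anticancer therapy or radiotherapy while on treatment may well have a higher risk. If so, the OS curve is too high. Section 8.2.9 keeps the study running after the main analysis specifically for response duration and OS, so these later data are what the extended follow-up is for. Vital status that was never collected may be hard to recover.

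**Working it through.** **1. The passages side by side.**

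| Trigger | Instruction to remove | Instruction to continue |
|---|---|---|
| Other anticancer therapy or radiotherapy in Screening or Treatment | 5.5.2: leaves the trial | 5.5: trial therapy may have to stop; 7.1.1.6.3, 7.1.5.4.3 and note 3 of 6.1: new anticancer therapy leads to survival follow-up; 1.0 and 2.1: everyone followed for OS |
| Live vaccine or non-permitted glucocorticoid | 5.5.2: leaves the trial | 5.5, 1.0 and 2.1 as above |
| Pregnancy | 5.7.3: leaves the study | 5.8: stops treatment only; 1.0 and 2.1 as above |

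Sections 1.0 and 2.1 allow survival contact to end only at death, consent withdrawal or end of study. Neither removal trigger is on that list. End of study for a subject is the latest of marketing approval, completed safety follow-up and loss of the chance of a second course, so a subject removed before approval has not reached it.

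**2. The plan's own figure.** The plan gives no event count or power for OS. The only figure to reproduce is the ORR test: 28 subjects, null rate 10%, true rate 35%, success at 7 or more (Section 8.2.7).

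- P(X ≥ 7 | n = 28, p = 0.10) = 0.0179, below 0.025. A cut-off of 6 gives 0.055, so 7 is the minimum.
- P(X ≥ 7 | n = 28, p = 0.35) = 0.908, which matches the stated 90% or so.

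None of these inputs depends on the removal wording.

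**3. Size of the OS bias.** The number removed and their later hazard are not in the documents, so these are assumptions:

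- 28 subjects; a fraction f = k/28 of those at risk is removed, and censored, at month 3.
- Exponential survival with 12-month OS of 80% in the others. The level is borrowed for illustration from the one-year figure quoted for the earlier study in Section 4.1.1.
- After month 3 the removed subjects have HR times the hazard of the others.

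Formulae:

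- Monthly hazard h = −ln(0.80)/12 = 0.0186.
- S(3) = exp(−3h) = 0.946; survival from month 3 to 12 in the others = exp(−9h) = 0.846; in the removed = exp(−9h·HR) = 0.716, 0.512 and 0.366 for HR 2, 4 and 6.
- Kaplan-Meier with removal as censoring: 0.946 × 0.846 = 0.800.
- True value: 0.946 × [(1 − f) × 0.846 + f × exp(−9h·HR)].
- Bias = 0.946 × f × [0.846 − exp(−9h·HR)].

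Example, k = 4 and HR = 4: 0.946 × (4/28) × (0.846 − 0.512) = 0.045.

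| Removed | HR 1 | HR 2 | HR 4 | HR 6 |
|---|---|---|---|---|
| 2 of 28 (7%) | 0 | 0.9 | 2.3 | 3.2 |
| 4 of 28 (14%) | 0 | 1.8 | 4.5 | 6.5 |

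Entries are percentage points by which 12-month OS is overstated. For scale, the binomial standard error at 80% with 28 subjects is √(0.8 × 0.2/28) = 0.076, or 7.6 points.

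**The case against.** The best defence is that the protocol, read whole, already answers the question. Section 5.5.2 covers only Screening and Treatment and ends by saying that nothing is prohibited in post-treatment follow-up. A subject who first stops for progression and later has chemotherapy never meets the removal sentence and is sent to survival follow-up by three separate passages. This stands. A reader might infer that a large share of progressing subjects, 40% say, would be lost and the bias would be correspondingly large; the documents do not support that.

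Other stronger readings also fail or shrink:

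- *Poor-prognosis subjects are deleted from OS.* In general they are censored, not deleted. Section 8.1.1 defines the FAS more narrowly than Section 8.2.4.1, and under 8.1.1 a subject removed before any post-baseline scan, for a reason other than progression or a drug-related AE, would fall outside it. That comes from the disagreement between the two FAS definitions, a separate matter.
- *Every removal is prognostic.* Pregnancy and live vaccines need not be, and some radiotherapy is allowed after Sponsor consultation.
- *Section 5.8 permits no other exit.* Its opening paragraph also lets the investigator or Sponsor withdraw subjects at discretion. The clearest conflict is therefore with Sections 1.0 and 2.1; against 5.8 it is the pregnancy item.
- *Safety windows are lost.* Sections 7.2 and 7.2.3.1 run them from cessation of treatment, Section 7.1.5.4.1 makes the 30-day visit mandatory, Section 7.1.4.1 requires final-visit activities and AE follow-up on leaving, and Section 5.7.3 itself requires at least monthly contact during pregnancy.

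What survives is that a site must overrule the plain words of 5.5.2 to comply with 2.1, and nothing tells it which sentence prevails.

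**Conclusion.** The conflict is real and is in current text. Its likely effect is modest: upward bias in a secondary, descriptive OS estimate, and only if sites apply 5.5.2 literally and the removed subjects have a worse outlook. Under the stated assumptions the overstatement of 12-month OS is about 1 to 6.5 points, less than one standard error, and zero if hazards are equal. The removal count, timing and hazard ratios are assumptions, not document figures.

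A reader might infer that the primary analysis is compromised. It is not: the wording itself leaves the ORR alpha of 0.0179, the power of 0.908 and the 7-of-28 rule as they are. The point is worth correcting because the correction is nearly free.

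**What to change.** Reconcile Sections 5.5.2 and 5.7.3 with Sections 1.0, 2.1, 5.5, 5.8, 7.1.1.6.3 and 7.1.5.4.3. In both sentences, make clear that the subject leaves treatment as the protocol's own discontinuation rules provide, not the trial, and that the safety follow-up and telephone survival contact already planned continue unless consent is withdrawn.

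This proposes no rule on whether or when treatment stops, on imaging, or on any other clinical management. Where 5.5 and 5.5.2 differ on those matters, the sponsor should settle the difference.

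The cost is two wording changes. No visits are added, since telephone contact is already planned for all subjects, and sample size, alpha, power and the success rule stay as they are. With vital status still collected, the bias from censoring at removal disappears.

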## 5.6 Rescue Medications & Supportive Care

### 5.6.1 Supportive Care Guidelines

Subjects should receive appropriate supportive care measures as deemed necessary by the treating investigator. Suggested supportive care measures for the management of adverse events with potential immunologic etiology are outlined below. Where appropriate, these guidelines include the use of oral or intravenous treatment with corticosteroids as well as additional anti-inflammatory agents if symptoms do not improve with administration of corticosteroids. Note that several courses of steroid tapering may be necessary as symptoms may worsen when the steroid dose is decreased. For each disorder, attempts should be made to rule out other causes such as metastatic disease or bacterial or viral infection, which might require additional supportive care. The treatment guidelines are intended to be applied when the investigator determines the events to be related to pembrolizumab.

Note: if after the evaluation the event is determined not to be related, the investigator does not need to follow the treatment guidance (as outlined below). Refer to Section 5.2.1 for dose modification.

It may be necessary to perform conditional procedures such as bronchoscopy, endoscopy, or skin photography as part of evaluation of the event.

- **Pneumonitis:**
  - For **Grade 2 events**, treat with systemic corticosteroids. When symptoms improve to Grade 1 or less, steroid taper should be started and continued over no less than 4 weeks.
  - For **Grade 3-4 events**, immediately treat with intravenous steroids. Administer additional anti-inflammatory measures, as needed.
  - Add prophylactic antibiotics for opportunistic infections in the case of prolonged steroid administration.
- **Diarrhea/Colitis:**

Subjects should be carefully monitored for signs and symptoms of enterocolitis (such as diarrhea, abdominal pain, blood or mucus in stool, with or without fever) and of bowel perforation (such as peritoneal signs and ileus).

  - All subjects who experience diarrhea/colitis should be advised to drink liberal quantities of clear fluids. If sufficient oral fluid intake is not feasible, fluid and electrolytes should be substituted via IV infusion. For Grade 2 or higher diarrhea, consider GI consultation and endoscopy to confirm or rule out colitis.

- For **Grade 2 diarrhea/colitis**, administer oral corticosteroids.
- For **Grade 3 or 4 diarrhea/colitis**, treat with intravenous steroids followed by high dose oral steroids.
- When symptoms improve to Grade 1 or less, steroid taper should be started and continued over no less than 4 weeks.
- **Type 1 diabetes mellitus (if new onset, including diabetic ketoacidosis [DKA]) or  $\geq$  Grade 3 Hyperglycemia, if associated with ketosis (ketonuria) or metabolic acidosis (DKA)**
  - For **T1DM** or **Grade 3-4** Hyperglycemia
    - Insulin replacement therapy is recommended for Type I diabetes mellitus and for Grade 3-4 hyperglycemia associated with metabolic acidosis or ketonuria.
    - Evaluate patients with serum glucose and a metabolic panel, urine ketones, glycosylated hemoglobin, and C-peptide.
- **Hypophysitis:**
  - For **Grade 2** events, treat with corticosteroids. When symptoms improve to Grade 1 or less, steroid taper should be started and continued over no less than 4 weeks. Replacement of appropriate hormones may be required as the steroid dose is tapered.
  - For **Grade 3-4** events, treat with an initial dose of IV corticosteroids followed by oral corticosteroids. When symptoms improve to Grade 1 or less, steroid taper should be started and continued over no less than 4 weeks. Replacement of appropriate hormones may be required as the steroid dose is tapered.
- **Hyperthyroidism or Hypothyroidism:**

Thyroid disorders can occur at any time during treatment. Monitor patients for changes in thyroid function (at the start of treatment, periodically during treatment, and as indicated based on clinical evaluation) and for clinical signs and symptoms of thyroid disorders.

  - **Grade 2** hyperthyroidism events (and **Grade 2-4** hypothyroidism):
    - In hyperthyroidism, non-selective beta-blockers (e.g. propranolol) are suggested as initial therapy.
    - In hypothyroidism, thyroid hormone replacement therapy, with levothyroxine or liothyroinine, is indicated per standard of care.

- **Grade 3-4** hyperthyroidism
  - Treat with an initial dose of IV corticosteroid followed by oral corticosteroids. When symptoms improve to Grade 1 or less, steroid taper should be started and continued over no less than 4 weeks. Replacement of appropriate hormones may be required as the steroid dose is tapered.
- **Hepatic:**
  - For **Grade 2** events, monitor liver function tests more frequently until returned to baseline values (consider weekly).
    - Treat with IV or oral corticosteroids
  - For **Grade 3-4** events, treat with intravenous corticosteroids for 24 to 48 hours.
  - When symptoms improve to Grade 1 or less, a steroid taper should be started and continued over no less than 4 weeks.
- **Renal Failure or Nephritis:**
  - For **Grade 2** events, treat with corticosteroids.
  - For **Grade 3-4** events, treat with systemic corticosteroids.
  - When symptoms improve to Grade 1 or less, steroid taper should be started and continued over no less than 4 weeks.
- **Management of Infusion Reactions:** Signs and symptoms usually develop during or shortly after drug infusion and generally resolve completely within 24 hours of completion of infusion.

**Table 4** below shows treatment guidelines for subjects who experience an infusion reaction associated with administration of pembrolizumab (MK-3475).

